### Patient and caregiver health care experience

**The Patient Activation Measure.** The Patient Activation Measure is a validated PRO measure developed to evaluate the engagement of patients in their care. The development process included conceptual definition and item generation through patient focus groups, literature review, and expert panel consensus. Psychometric evaluation of the scales was performed using Rasch psychometric methods, and further validation was completed in a large national sample. This measure includes items querying patients about their confidence (self-efficacy) and knowledge to take action specific to their health. Items include *“I am confident I can tell when I need to get medical care”* and *“I am confident I can take actions that will prevent or minimize symptoms or problems.”* This PRO measure was selected because it evaluates a key concept of interest in our study, was rigorously developed with qualitative and quantitative methods, and has strong psychometric properties. PAM yields only a total score that will be used in the analysis.

**The Caregiver Reaction Assessment.** The Caregiver Reaction Assessment is a validated instrument designed to assess the impact of caregiving on disrupted schedules, self-esteem, and financial and health problems. The Caregiver Reaction Assessment assesses specific aspects of the caregiving situation, including both negative and positive dimensions of caregiving reactions. The Caregiver Reaction Assessment (CRA) consists of 5 subscales, 4 of which are negative and 1 positive. The negative subscales have higher scores indicating higher level of burden, rated from 1 (strongly disagree) to 5 (strongly agree). The four negative subscales are: Impact on

Schedule (5 items), Impact on Health (4 items), Lack of Family Support (5 items) and Impact on Finances (3 items). The positive subscale, Caregiver's Self Esteem (7 items), has lower scores indicating higher levels of burden rated from 1 to (strongly disagree) to 5 (strongly agree).

Five dimensions of caregiver reactions were identified through exploratory factor analysis: the impact of caregiving on disrupted schedules, financial problems, lack of family support, health problems, and self-esteem. Reliability analyses show that standardized Cronbach's alphas vary between 0.62 and 0.83 for the separate subscales, indicating sufficient internal consistencies and that construct validity is supported. This measure was selected because it is well-targeted to our outcomes of interest and was developed among partners of patients with cancer.

**The PRO-CTCAE Anxiety Items.** The PRO-CTCAE Anxiety scale consists of three items scored 0–4, for a full-scale range of 0–12 (see pages 11 and 12 for PRO-CTCAE development and validation). These include: “How often do you feel anxiety?” “What was the severity of your anxiety at its worst?” and “How much did anxiety interfere with your usual or daily activities?”

**Qualitative patient and caregiver interviews** will be conducted in a subsample of patients and their caregivers throughout the study. After study consent, patients and caregivers will be invited to volunteer for possible future in-depth, semistructured qualitative interviews (either individual or in group form). We will approach patients (and caregivers) numerous times throughout the course of the study until data saturation. We will select patients from both randomized cohorts and will seek to interview a heterogeneous patient sample (i.e., patients representing the full spectrum of established potential participants (patients and caregivers) for possible interviews in order to examine and evaluate both patient engagement and caregiver burden (SA2a, SA2c) throughout the study. We will ensure that we have a selection of volunteers that represent a range of procedure types and ages for all qualitative interviews.

The entire study team, including patient and caregiver partners and advocacy organization members will contribute to the development of the interview guide (see Appendices I and J). [name] will conduct the interviews, which will be recorded and transcribed verbatim. The data will be coded using a line-by-line approach, where all concepts will be labeled by major and minor themes. Coding will take place as soon as possible after an interview so that findings can inform subsequent interviews in an iterative fashion. Codes (i.e., patient quotations) and their major and minor themes will be organized and analyzed using NVivo qualitative analysis software (QSR International). Patient characteristics (e.g., age, disease condition, procedure) will also be incorporated into the qualitative database to help identify groups that might experience the system differently (e.g., elderly patients or those with lower education levels). Interviews will continue until data saturation is reached (i.e., no new themes identified). On the basis of our team's previous experience with qualitative research studies, we anticipate reaching data saturation after approximately 30 patient and 30 caregiver interviews.

## **5.0 CRITERIA FOR SUBJECT ELIGIBILITY**

All patients scheduled for ambulatory cancer surgery at JRSC will be eligible. For patients with disabilities that make it difficult to complete the electronic surveys (e.g., visual impairment, hand function problems), we will train caregivers to help with completion of the survey. The PRO-CTCAE questions have already been tested to ensure that they will be easily understood by patients with low literacy levels.

Additionally, patients will be asked to identify a caregiver to participate in a 2-week and 2-month follow-up questionnaire and possibly in a qualitative interview. Caregivers will be approached and consented to participate.

### **5.1 Subject Inclusion Criteria**

- All patients >18 years of age who are scheduled for ambulatory cancer surgery at JRSC, and their caregivers, will be eligible for study participation.

### **5.2 Subject Exclusion Criteria**

**The following criteria apply to both patients and their caregivers:**

- Inability to speak English
- Inability to access a computer, tablet, or mobile phone
- For patients: not interested in/unable to sign up for the MyMSK Patient Portal
- For caregivers: Unable to provide an email address
- Cognitive impairment that prohibits informed consent or understanding of the study protocol

## **6.1 RECRUITMENT PLAN**

### **Patient Recruitment Plan**

All patients who are scheduled for surgery at JRSC will receive IRB/PB-approved written educational materials that describe the study (see Appendices D and H) via the MyMSK Patient Portal, by email, or by a letter mailed to their home (see Appendices F and G). If a patient is not yet signed up for the MyMSK Patient Portal, the study team will also include a brief document that instructs patients how to register (see Appendix K).

Patients will be advised that they will be approached to participate in this study by phone prior to surgery, at their next clinic appointment, or in person on the day of their surgery. They will be encouraged to read through the information carefully and to also consider whether there is a caregiver in their life who can be approached to participate in the caregiver portion of the study. The materials will provide contact information for the CRC and the PI of the study in case patients have questions they would like addressed before the day of surgery. The CRC will then attempt to contact eligible patients by phone before surgery. Using an IRB-approved verbal consent script, the CRC will explain the study to

patients. Written consent will not be obtained; rather, the CRC will document the patient's verbal consent.

If the CRC is not able to contact the patient by email, Patient Portal, or phone prior to the day of surgery, she/he will approach the patient at one of their upcoming clinic appointments or when they arrive at JRSC for surgery. The CRC will describe the study in person, again using the IRB-approved verbal consent script. Patients will be approached on the day of their surgery in the waiting area, and the consent discussion will happen in a private consultation room on the third floor at JRSC. Patients will not be approached in the pre-operative area, and will be given as much time as needed to decide whether or not they will participate in the study.

### **Caregiver Recruitment Plan**

Patients will be asked at the time of consent to identify a caregiver whom they would like to be actively involved in their recovery and may be interested in participating in the study. The CRC will obtain the caregivers' contact information from the patient.

Caregivers can be contacted in several ways:

- 1) If the caregiver is present in clinic with the patient, the CRC will approach the caregiver at that time.
- 2) If the patient suggests contacting the caregiver by email or phone, the CRC will proceed to contact the caregiver using the preferred method of contact provided by the patient.
  - a. If personal email is preferred, the caregivers will be provided written education materials regarding the study via email (see Appendices E and H). Caregivers will be advised that they will be approached to participate in this study by phone prior to surgery or in person on the day of the patient's surgery. The materials will also provide contact information for the CRC and the PI for the study, in case caregivers have questions they would like addressed before the day of surgery.
  - b. If phone is preferred, the CRC will call the caregiver and invite them to participate.
- 3) If no contact is made prior to surgery, or if the patient/caregiver requests to be approached on the day of surgery, the CRC will approach the caregiver on the day of surgery.

Given the extent to which caregivers are already integrated into the clinical experience at JRSC, we estimate that more than 50% of caregivers (n=1,375) will agree to participate in the study.

## **7.0 ASSESSMENT/EVALUATION PLAN**

The Recovery Tracker will be completed by all patients for up to 30 days following their surgery. Patients will be sent the Patient Activation Measure (PAM) through the MyMSK Patient Portal (see Appendices A and H). In the event the electronic PAM survey is not available, a hardcopy version will be provided to the patient to complete.

Caregivers will be asked to provide their email and will be sent the Caregiver Reaction Questionnaire and a brief demographic questionnaire through REDCap (see Appendices B, C, and H). In the event the electronic survey is not available, a hardcopy questionnaire will be provided to the caregiver to complete.

	# of Items	Pre-Op (day of consent - POD1)	POD 1-10	POD14 (+7/-3 days)	POD30 (+/-10 days)	POD60 (+/- 14 days)
Patient						
Recovery Tracker (including PRO-CTCAE symptoms and anxiety items, and additional questions)	20		Daily		Available to complete if desired (POD11-30)	
Emergency Department Visits					X	
Readmission					X	
Adverse Events					X	
Patient Activation Measure	10	X		X		X
Patient Interviews					X	
Caregiver						
Caregiver Reaction Assessment	24			X		X
Caregiver Interviews					X	

## 8.0 TOXICITIES/SIDE EFFECTS

There are minimal risks to all subjects involved in any phase of the study. Patients who indicate excessive anxiety or distress will be offered a referral to an MSKCC psychiatry professional. If severe symptoms are reported, patients in both groups will be instructed to immediately contact their physician's office or seek medical attention and the clinical team be alerted.

## 9.0 PRIMARY OUTCOMES

The primary outcome for SA1, emergency department visits up to 30 days after ambulatory cancer surgery, is important to patients because emergency department visits are time-consuming and may increase anxiety and caregiver burden. It is relevant to health care systems and clinicians because such visits are inefficient and costly and may erode trust between the patient and provider.

## 10.0 CRITERIA FOR REMOVAL FROM STUDY

Participants will be considered off-study if they do not undergo an eligible procedure, their surgery is not performed at the Josie Robertson Surgery Center or they are not discharged within 48 hours of their surgery (POD2). All other participants will remain on study to be analyzed using an intent-to-treat approach.

## 11.0 BIostatistics

The data analysis plan corresponds to our Specific Aims as described on pages 9 and 10. All statistical analyses will be led by coinvestigator [name] (who has been an investigator on more than 20 randomized trials and has written extensively on trial methodology) and study consultant [name] (who contributed to the development and is experienced in analysis of the PRO-CTCAE items). The enrollment time frame for this protocol is three years.

### Power calculation

Sample size and power calculations were based on the primary outcome, the difference in emergency department visits without admission, between the Enhanced Feedback and Team Monitoring arms. On the basis of current MSKCC data, we expect for every 1,000 eligible patients treated surgically at JRSC, 69 patients will make emergency department visits. We also estimate that of these 69 patients, 28 will require readmission, and hence 41 will have visits the emergency department unnecessarily. The majority of such unnecessary visits are related to concerns about symptoms, which might be avoided if patients have a better understanding of expected symptom severity. Using a traditional alpha of 5% and an event rate of 4.1% in the control group, the power to detect different relative risk reductions is given below for a total sample size of 2,750 patients.

Relative Risk Reduction	Power
33%	45%
40%	64%
50%	85%
67%	96%

The primary analysis will compare, between groups, the proportion of patients with at least 1 emergency department visit without admission within 30 days (SA1a) of surgery by logistic regression with randomization strata as covariates. A difference between proportions will be calculated along with a 95% CI by applying the odds ratio from the regression to the event rate in the control group. A similar statistical approach will be taken for the proportion of patients referred to pain management and unplanned clinic visits (SA1b). For nursing follow-up calls (SA1b), phone referrals (SA1b) and rates of adverse events (SA1b), we will use both a binary approach (e.g., at least 1 nursing call vs. no nursing call) and analysis of count data using negative binomial regression with randomization strata as covariates. For all binary endpoints, an event will be counted only if it occurs within 30 days of surgery.

For the endpoints of patient engagement (SA2a) and caregiver burden (SA2c), we will use linear regression with randomization strata as covariates for each subscale separately. For all analyses, we will report an estimate of the difference between groups along with a 95% CI and a two-sided P value for the null hypothesis of no difference between groups. For the endpoint of patient anxiety (SA2b), as measured by the PRO-CTCAE, we will enter daily anxiety scores as a continuous outcome variable into a longitudinal mixed effects model with time, treatment, and treatment by time interaction as predictors and randomization strata as covariates. As all data are collected after randomization, both the treatment term and the treatment by time interaction term are valid indicators of a treatment effect. We hypothesize that initial anxiety will be similar between groups and will be related to immediate postoperative concerns. Subsequent anxiety may be related to emergent symptoms, whether they are considered worrying and how they are dealt with. Hence, we will treat the time by treatment interaction as the primary hypothesis for the purpose of establishing the treatment effect of enhanced feedback on patient anxiety.

In exploratory analysis, the mean of each PRO-CTCAE item (0–4 scale) will be compared between groups during the 10-day post-surgery daily reporting period using the same longitudinal mixed effects model described above for anxiety with time, treatment, and treatment by time interaction as predictors and randomization strata as covariates. All available data will be used in these models. This likelihood-based approach to the analysis of longitudinal PRO data provides valid estimates of intervention effects in the presence of ignorable missing data and is known to be robust to nonignorable missing data if covariates and previous values of the outcome explain much of the missingness.

Supplemental analysis will also employ longitudinal mixed ordinal logistic models to compare ordinal PRO-CTCAE scores between arms.

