### Methodological approach

The study is a parallel group trial, with 1:1 procedure-stratified randomization between the Team Monitoring and Enhanced Feedback arms. The two groups will differ by how their self-reported symptom information is handled: Enhanced Feedback (system displays the patient's self-reported symptom data alongside expected norms for that procedure, and patient initiates care escalation) vs. Team Monitoring (the patient completes self-reported symptom assessment as per standard care at MSKCC; the clinical team contacts the patient if symptoms are above expected levels or appear to be worsening). Note: When patients report severe symptoms in either group, the care team will receive an alert and patients will also be instructed to immediately contact the clinical team. (Alerts to the clinical team can only be monitored during business hours, so all patients must seek care after hours in the current standard care fashion.) Our study design follows CONSORT and PCORI standards, including patient engagement, research methods, data integrity and

analysis (including stratification by surgical procedure), handling of missing data, and heterogeneity of treatment effect.

**Primary outcome:** The primary outcome for Aim 1, emergency department visits up to 30 days after ambulatory cancer surgery, is important to patients because emergency department visits are time-consuming and may increase anxiety and caregiver burden. It is relevant to health care systems and clinicians because such visits are inefficient and costly and may erode trust between the patient and provider.

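### The last row of the power table does not follow from its inputs: a 67% relative risk reduction has about 99% power, not 96%

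*Combined protocol and SAP*

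**What the plan says.** The Power calculation part of section 11.0 derives the control event rate from institutional data. Of every 1,000 eligible patients, 69 are expected to visit an emergency department, and "of these 69 patients, 28 will require readmission, and hence 41 will have visits the emergency department unnecessarily". The inputs to the table are then given as "Using a traditional alpha of 5% and an event rate of 4.1% in the control group", and "the power to detect different relative risk reductions is given below for a total sample size of 2,750 patients". The table reads:

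| Relative risk reduction | Stated power |
|---|---|
| 33% | 45% |
| 40% | 64% |
| 50% | 85% |
| 67% | 96% |

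The outcome is binary: the primary analysis compares "the proportion of patients with at least 1 emergency department visit without admission within 30 days (SA1a) of surgery by logistic regression", with the randomization strata as covariates. Section 4.2 (Methodological approach) fixes the allocation: "The study is a parallel group trial, with 1:1 procedure-stratified randomization between the Team Monitoring and Enhanced Feedback arms". Section 11.0 also says that analyses will report "a two-sided P value for the null hypothesis of no difference between groups". No test formula, continuity correction or allowance for dropout is given for the table.

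**The concern.** Power climbs steeply with effect size at this sample size. A trial with 85% power at a 50% reduction should be close to certain to detect a 67% reduction, so 96% looks low beside the row above it. This is the trial's only sample-size table. If one entry does not follow from the inputs printed next to it, a reader who checks the table cannot reproduce it. Because no method is named, that reader also cannot tell whether the effect or the power was mistyped. In terms of type II error, the printed row implies 4%, against about 0.9% under the calculation that fits the other rows.

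**Working it through.** **Inputs**

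- Control rate p0 = (69 − 28)/1,000 = 0.041 (section 11.0).
- Total 2,750 (section 11.0) at 1:1 (section 4.2), so n = 1,375 per arm.
- Alpha 5% (Power calculation), taken as two-sided because section 11.0 specifies two-sided P values. The critical value is z = 1.960.
- Enhanced Feedback rate p1 = p0 × (1 − RRR), where RRR is the relative risk reduction. At 67%, p1 = 0.041 × 0.33 = 0.01353.

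**Formulas.** Let d = p0 − p1 and p̄ = (p0 + p1)/2. Let s0 = √[2p̄(1 − p̄)/n] be the standard error under the null, and s1 = √{[p0(1 − p0) + p1(1 − p1)]/n} the standard error under the alternative.

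- Continuity-corrected: power = Φ[(d − 1/n − 1.960·s0)/s1].
- Pooled, uncorrected: the same without 1/n.
- Wald on the log odds ratio: power = Φ[log OR/SE − 1.960], with SE = √{1/[n·p0(1 − p0)] + 1/[n·p1(1 − p1)]}.

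**Reproducing the plan's figures**

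| RRR | Stated | Continuity-corrected | Fisher exact | Pooled z | Wald log OR |
|---|---|---|---|---|---|
| 33% | 45% | 45.5% | 45.6% | 49.6% | 49.1% |
| 40% | 64% | 63.6% | 64.1% | 67.5% | 66.6% |
| 50% | 85% | 85.2% | 86.0% | 87.6% | 86.3% |
| 67% | 96% | 99.1% | 99.4% | 99.3% | 98.8% |

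The continuity-corrected calculation matches the first three rows to within half a point, so it, or something close to it, is the likely source. No method in the table brings the last row near 96%.

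**The last row in full (continuity-corrected).**

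- d = 0.041 − 0.01353 = 0.02747; 1/n = 0.000727; p̄ = 0.027265.
- s0 = 0.006211; s1 = 0.006189.
- (0.02747 − 0.000727 − 1.960 × 0.006211)/0.006189 = 2.354, and Φ(2.354) = 99.1%.
- Expected events are 1,375 × 0.041 = 56.4 against 1,375 × 0.01353 = 18.6.

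**What would make 96% true?**

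- *Rounding of two thirds.* With RRR = 2/3, power is 99.0% corrected, 99.3% pooled and 98.7% Wald.
- *A one-sided test.* Power rises to 99.7% (pooled).
- *Fewer evaluable patients.* Section 10.0 removes some participants ("Participants will be considered off-study if they do not undergo an eligible procedure", among other reasons). The plan gives no expected number, so 2,550 and 2,500 are assumed here. With 2,550, power at 67% is 98.2% Wald, 98.6% corrected and 98.9% pooled. With 2,500 it is 98.0%, 98.4% and 98.8%.
- *A smaller sample for the whole table.* Under the corrected formula, the total N implied by each row is 2,719, 2,774, 2,736 and 2,072. The first three sit around 2,750, and the last is 25% below it (2,072/2,750 = 0.753). At 2,072 patients the first three rows would be 34.9%, 50.5% and 73.1%.
- *A lower control rate.* The last row needs about 3.1% (corrected) in place of 4.1%. At that rate the first three rows would be about 35%, 50% and 73%.
- *A stricter alpha.* At 1% (pooled) the rows are 27%, 44%, 70% and 97%, so the first three fail.
- *A different effect.* At the stated inputs, 96% power is reached at a reduction of 59.4% (corrected), 59.7% (Wald) or 58.0% (pooled). A 60% reduction gives 96.4% corrected.

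Only a change to that row's own effect or power reconciles it with the other three.

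**The case against.** The strongest reply is that nothing depends on this entry. The plan names no row as its design target, the error understates power, and it sits at the largest effect listed. The sample size, the control rate and the primary analysis are the same whether the cell reads 96% or 99%. That is right, and it limits the point to a correction.

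A second reply is that the method is inferred. Rows 1 to 3 agree with the stated inputs if a continuity-corrected or Fisher calculation was used. Under the Wald log odds ratio, which is closer to the planned logistic regression, they would be 49.1%, 66.6% and 86.3%. Nor is continuity correction the only near fit: a pooled test with 2,500 patients gives 46.0%, 63.4% and 84.4%. This stands as a qualification on rows 1 to 3. It does not help the last row, which that same alternative puts at 98.8%.

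Third, the text available for review was extracted from a PDF, and 96 and 99 differ by one digit. The table is intact and nothing suggests a misreading, but a look at the source page is a sensible first step.

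Finally, no section mentions a 60% reduction. That reading fits the arithmetic but remains a question for the sponsor.

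**Conclusion.** The concern holds. At a 4.1% control rate, 1,375 per arm and two-sided 5%, power for a 67% reduction is 98.8% to 99.4% across the four methods tabulated, against a stated 96%. That is an understatement of about 3 points. The finding rests on the plan's own inputs and on reading the alpha as two-sided; a one-sided reading widens the gap. It does not depend on the choice of test. The statement that rows 1 to 3 are sound does depend on a continuity-corrected or similar calculation, which the plan does not name. The documents do not show whether the effect or the power in the last row is the wrong figure. Severity is minor.

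**What to change.** After a check against the source page and the original calculation, change the last row to 67% with 99% power. If the row was computed for a 60% reduction, relabel it 60% and keep 96%. Add one sentence naming the method behind the table, for example a two-sided continuity-corrected comparison of two proportions if that is what was used. If a different method was used, check rows 1 to 3 against it as well. The cost is one table cell and one sentence, with no change to the design, the sample size or the analysis.

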### **Sensitivity analyses to determine the impact of key assumptions and missing data**

The primary threat to validity is a larger than expected number of emergency department visits to outside institutions and reporting that varies systematically between groups (e.g., if patients in the Enhanced Feedback group are less likely to report a visit to a non-MSKCC emergency department). We will conduct sensitivity analyses by first examining whether the proportion of visits to MSKCC vs. non-MSKCC sites varies between groups. We will then determine the number and distribution of unreported emergency department visits that would need to have occurred to change our conclusions (e.g., if we reject the null hypothesis in favor of the experimental arm, we will determine the number of excess unreported visits in the experimental arm that would result in a  $P$  value  $\geq 0.05$ ).

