### **Reporting plan with assessments of internal and external validity**

This is a randomized trial with good allocation concealment, and therefore selection bias can be discounted. Patients, however, will not be blinded. This is not an important issue for the primary endpoint, which is emergency department visits, as this is objectively measured and not susceptible to reporting bias. The question of performance bias in terms of differential patient behavior is complicated by the fact that the *aim* of the trial is to change behavior. Performance bias by clinicians is, however, a concern. For instance, it is plausible that a nurse speaking to a study patient by phone in the days after discharge might make differential recommendations about the necessity of an emergency department visit depending on patient assignment. However, this is an unlikely scenario given the context of nursing care at MSKCC. Nurses call large numbers of patients, both those eligible for the trial (ambulatory care surgery) and those ineligible (e.g., complex operations requiring an in-patient stay), and they are unlikely to know which patients are and are not on trial. Patients might potentially reveal allocation to nurses during the phone call (e.g., “I saw on the website that...”). But, again, as a large number of nurses will be dealing with a large volume of patient calls, it is unlikely that allocation will bias the advice given to a significant extent.

Regarding external validity, the system is currently in use by MSKCC patients, but it is possible that these patients (a referral population in a major urban center) may have higher computer literacy, health literacy, or numeracy than the general population. We recognize that usability barriers that might seem trivial to a highly technology-focused audience can sometimes seem insurmountable for patients facing stress due to illness or treatment or for patients who face preexisting hurdles in terms of computer literacy, health literacy, or numeracy. As a result, we have built in a brief user-centered design stage supervised by coinvestigator [name] to review the existing platform in a systematic fashion, elicit constructive feedback from representative users, and perform rapid-cycle modifications to ensure usability and utility for users. We anticipate that this intensive user-centered design project will successfully adapt the existing instrument.

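### The primary outcome is emergency department visits in sections 4.2 and 9.0 but visits without admission in the powered and tested analysis, and nothing says which governs

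*Combined protocol and SAP*

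**What the plan says.** Section 4.2 (Methodological approach) introduces "The primary outcome for Aim 1, emergency department visits up to 30 days after ambulatory cancer surgery". Section 9.0, whose heading is Primary Outcomes, repeats it: "The primary outcome for SA1, emergency department visits up to 30 days after ambulatory cancer surgery, is important to patients". In section 11.0, the text on internal and external validity refers to "the primary endpoint, which is emergency department visits, as this is objectively measured and not susceptible to reporting bias". None of these three places restricts the outcome by admission, and none gives a rate.

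The Power calculation in section 11.0 describes "the primary outcome, the difference in emergency department visits without admission". It starts from 69 patients per 1,000 with an ED visit and reasons that "of these 69 patients, 28 will require readmission, and hence 41 will have visits the emergency department unnecessarily". The power table follows: "Using a traditional alpha of 5% and an event rate of 4.1% in the control group". The primary analysis then compares "the proportion of patients with at least 1 emergency department visit without admission within 30 days (SA1a) of surgery by logistic regression", with the randomization strata as covariates.

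The sensitivity analysis in section 11.0 looks for "the number and distribution of unreported emergency department visits that would need to have occurred to change our conclusions", again with no condition on admission. The Study outcomes table in section 4.3 lists ED visits and readmissions under SA1a and does not mark which measure is primary. Readmission is also a secondary outcome in section 4.2, but section 11.0 names no model for it.

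**The concern.** The section a reader consults for the primary outcome and the section that specifies the test describe different events. A patient whose only ED visit ends in admission is an event under sections 4.2 and 9.0 and a non-event under the primary analysis. On the plan's figures that is 28 of every 69 patients with an ED visit (41%).

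Three things are at stake. First, a report or registration written from section 9.0 would name an endpoint that was not the one tested. Second, with both wordings in the protocol, either result could be called primary after the data are seen. Third, admission happens after randomization. If Enhanced Feedback moved some patients from a non-admitted to an admitted visit, for example because they came later and sicker, the tested endpoint would fall and look like benefit. The plan does not commit to showing the results that would reveal this.

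**Working it through.** **Inputs.** Total 2,750 patients and a 4.1% control rate (Power calculation); 1:1 allocation (section 4.2), so n = 1,375 per arm; 5% alpha, two-sided as in the rest of section 11.0; 69, 28 and 41 patients per 1,000 with any, admitted-only and non-admitted ED visits (Power calculation). Check: 69 − 28 = 41, so 4.1%.

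**1. Which endpoint the power table uses.** For two proportions with continuity correction,

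power = Φ{ [ |p1 − p2| − 1/n − 1.96·√(2p̄(1−p̄)/n) ] / √[(p1(1−p1) + p2(1−p2))/n] }.

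For the 50% row, p1 = 0.041 and p2 = 0.0205: (0.01977 − 1.96 × 0.00658) / 0.00657 = 1.045, and Φ(1.045) = 85.2%. The plan states 85%.

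| Relative reduction | Stated | Non-admitted, 4.1% | Any ED, 6.9%, same relative fall | Any ED, admitted visits unchanged |
|---|---|---|---|---|
| 33% | 45% | 45.5% | 69.9% | 28.4% |
| 40% | 64% | 63.6% | 87.0% | 40.5% |
| 50% | 85% | 85.2% | 98.0% | 59.7% |
| 67% | 96% | 99.1% | 100% | 86.7% |

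The first three rows reproduce at 4.1% and not at 6.9%, so the table belongs to visits without admission. Without the continuity correction the 4.1% column is 49.6, 67.5, 87.6 and 99.3%.

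**2. The 67% row.** With p2 = 0.041 × 0.33 = 0.01353: (0.02674 − 1.96 × 0.00621) / 0.00619 = 2.35, which gives 99.1%. Pooled, unpooled, log odds ratio and Fisher exact versions, two-sided, give 98.8% to 99.4%. None gives 96%. With continuity correction, 96% corresponds to a reduction of about 59%.

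**3. How often the two definitions would disagree.** 400,000 trials per row were simulated with three classes per patient: no ED visit, non-admitted (control 0.041) and admitted (control 0.028). Each trial was tested on both endpoints with the unadjusted pooled z. Disagreement means P < 0.05 in favour of Enhanced Feedback on one endpoint only. The plan gives no effect on admitted visits, so two assumptions bracket it:

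| Row | Admitted visits unchanged | Admitted visits fall in proportion |
|---|---|---|
| 33% | 28% | 29% |
| 40% | 31% | 24% |
| 50% | 28–29% | 10–11% |
| 67% | 11% | 0.4% |

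Under the first assumption most disagreements are significant on non-admitted visits only; under the second, on any ED visit only. A stratum-adjusted check (Mantel-Haenszel score test, the 13 strata of section 12.3, assumed uneven stratum sizes and risks) gave 28/31/28/11% and 29/23/10/0.4%.

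**4. The unreported-visit analysis at the 50% row.** Expected control counts are 0.041 × 1,375 = 56 and 0.069 × 1,375 = 95. In the Enhanced Feedback arm they are 28 (non-admitted), 0.0485 × 1,375 = 67 (any, admitted unchanged) and 0.0345 × 1,375 = 47 (any, proportional fall). Events were added to Enhanced Feedback until the pooled-z P reached 0.05 or more:

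- Non-admitted, 56 vs 28: 10 patients.
- Any ED visit, 95 vs 67: 4 patients.
- Any ED visit, 95 vs 47: 24 patients.

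**The case against.** The strongest reply is that there is no real ambiguity about what will be tested. The Power calculation calls visits without admission both the primary outcome and the subject of the primary analysis. It gives the arithmetic, rationale, control rate, unit of count, time window and model. The background and design text also speaks of avoiding unnecessary visits, which fits. Sections 4.2 and 9.0 are near-identical rationale paragraphs with no rate and no test, and can be read as a broader label. This stands, and it limits the point to an unreconciled definition. It does not remove it: section 9.0 is the section headed Primary Outcomes, the validity text inside section 11.0 uses the broad wording too, and no sentence says which prevails.

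A reader might infer more than the documents support:

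- **That sections 4.2 and 9.0 imply 69 per 1,000.** They state no rate. The 69 appears only in the Power calculation, as a step towards 41.
- **That 10% to 31% of trials would reach a wrong conclusion.** Those figures compare the planned test with an any-ED test that the plan does not specify, under assumed effects on admitted visits.
- **That the unreported-visit analysis cannot be computed.** It refers to rejecting the null hypothesis, and the only primary test is the one in the Power calculation. It can be run on that definition; a clarifying phrase is all it lacks.
- **That a patient with both kinds of visit is unclassified.** At least one visit without admission makes that patient an event.
- **That the 67% row is evidence of the mismatch.** It fits neither definition and understates power.

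**Conclusion.** The inconsistency is real. Three places name ED visits without qualification; the one place that specifies a test uses visits without admission; nothing reconciles them. The sample size, the test and the first three power rows are coherent with the narrower endpoint, so the design is not undermined. The exposure lies in reporting: the named and the tested endpoint could differ, with disagreement of roughly 10% to 31% at the 33% to 50% rows and 11% or less at the 67% row. That range rests on the plan's 41 and 28 per 1,000 and on the two assumed effects on admitted visits.

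The 67% power entry is a separate error: 96% should be about 99% at 4.1% and 1,375 per arm. The missing readmission model and the absence of an any-ED analysis are lesser gaps and do not carry the point.

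**What to change.** Before outcome data are analysed:

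1. State one primary endpoint in identical words in section 4.2, section 9.0, and the Power calculation and validity text of section 11.0. Mark it as primary in the Study outcomes table.
2. If ED visit without admission is kept, correct the 67% row to about 99%. If any ED visit is chosen, recompute the whole power table.
3. Add to the sensitivity analysis that the unreported visits counted are those that are events under the primary definition.
4. If ED visit without admission is kept, report any ED visit and readmission within 30 days beside it as supportive analyses. Use the same stratum-adjusted logistic model with 95% confidence intervals, so that a shift from non-admitted to admitted visits would be visible.

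The cost is wording, one table mark, one power entry and two more secondary analyses on data already collected. No extra patients are needed, and if the narrower endpoint is kept, the power of the primary test does not change.
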